1.2 Purpose of the analyses

The purpose of this SAP is to outline the pre-planned analyses to be completed to support the main publication of the analysis of the trial and is based on version 2.0 of the protocol. Versions of the SAP will be tracked. This document contains a review of the study design, general statistical considerations, and statistical analysis methods for antibody outcomes. The reader of this SAP is encouraged to also review the study protocol (ClinicalTrials.gov Identifier: NCT04478370) for details on conduct of the study and the operational aspects of clinical assessments.

2 Study Objectives and Endpoints

2.1 Study Objectives

Primary objectives:

The primary objective of this study is to identify and validate biomarkers of exposure to bites of *An. dirus, An. maculatus, An. minimus, Ae. aegypti* and *Ae. albopictus.*

Secondary objectives:

- 1. To characterize the relationship between levels of mosquito exposure and humoral response.
- 2. To assess the feasibility of using dry blood spots made from capillary blood for the monitoring of exposure to bites of mosquito vectors of malaria and dengue.

2.2 Endpoints

Primary endpoints:

1. The levels (continuous OD (405nm)) and seroprevalence (binary) of total IgG antibodies against *Anopheles* and *Aedes* species-specific salivary peptides mesured in human serum; including gSG6-P1, minSG6-P1, macSG6-P1, dirSG6-P1, aegN-term34kDa, albN-term34kda.

Secondary endpoints:

- 1. The levels (continuous OD (405nm)) and seroprevalence (binary) of antibodies (including different isotypes and subclasses) against *Anopheles* and *Aedes* species-specific salivary peptides; including gSG6-P1, minSG6-P1, macSG6-P1, dirSG6-P1, aegN-term34kDa, albN-term34kda.
- 2. The levels (continuous OD (405nm)) and seroprevalence (binary) of antibodies (any isotype or subclasses) against novel *Anopheles* and *Aedes* species-specific salivary peptides mesured in human serum.
- 3. The levels (continuous OD (405nm)) and seroprevalence (binary) of antibodies against *Anopheles* and *Aedes* species-specific salivary peptides mesured in human dried blood spots.

3 Study Methods

3.1 General Study Design and Plan

Study setting

The study will be conducted at the research center of the Shoklo Malaria Research Unit (SMRU) in Mae Sot, Thailand. Critical to the trial design, Mae sot is a small town in Thailand where *Anopheles* mosquitoes have disappeared after decades of development and urbanization (27). Therefore, people who live in Mae Sot are not exposed to *Anopheles* bites if they do not travel in rural areas located outside the city.

Eligibility criteria

Volunteer eligibility to the study will be assessed using the criteria presented in Table 1. Intervention

Participants will be exposed to bites of laboratory-adapted colonies of An. minimus (s.s.), An. maculatus (s.s.), An. dirus (s.s.), Ae. aegypti or Ae. albopictus weekly for six weeks (seven challenges per participant in total). Participants in the low-exposure arms will be challenged on each occasion with five mosquito bites (35 bites in total), those in the high-exposure arms will be challenged once with five bites and then six times with 50 bites (305 bites in total). In order to assess participant skin reactions to mosquito bites, three bites will be administered on one participant arm using single mosquitoes in 50 mL tubes topped with netting material. The remaining mosquitoes will be put into plastic cups of 10 cm in diameter topped with netting material and offered to feed on participant counter arm, calf, thigh or back skin. The mosquitoes will be left undisturbed and allowed to feed for 30 minutes. The number of bites actually received by the participant will be assessed by counting the number of engorged mosquitoes at the end of the exposure time. If the mosquitoes are not all successfully engorged, the participant will be exposed to additional mosquitoes using the same procedure in order to reach the target number of bites. All challenges will be performed with 5- to 7-day-old starved nulliparous female imagoes (i.e., that have never blood fed before) of laboratory-adapted mosquito colonies reared in insectaries. Participants with hypersensitivity to mosquito bites will be withdrawn from the study. In order to increase adherence to the study protocol, the study coordinator will call participants on the day before a scheduled visit and remined them about the appointment. Participants who miss a visit will be given the opportunity to come for a retake visit until the day of the next scheduled visit. All participants will be provided antipruritic medication (chlorphenoxamine cream and cetirizine pills) to relieve itching from mosquito bites. Participants will be informed during the screening visit about the importance of avoiding being bitten by Anopheles mosquitoes during the study and how to do so. They will be provided with an insecticide-impregnated mosquito bed net (PermaNet 2.0°, Vestergaard) and skin repellent (N,N-diethyl-meta-toluamide, D.E.E.T., 20%). They will be asked not to travel to rural areas and the travel history will be recorded at every visit.

Immunological assays

Previous wok by Poinsignon, et al. (28) generated synthetic peptides of the An. gambiae salivary protein gSG6, and identified the peptide of the P1 region (gSG6-P1) as an immunogenic biomarker of exposure to Anopheles bites. As the homologues from the primary malaria vectors of Southeast Asia share varied sequence identity to gSG6-P1 (Table 1), we used the published sequences of the SG6 proteins (24) to synthesise species-specific Anopheles salivary antigens corresponding to the SG6-P1 region of An. gambiae (gSG6-P1), An. minimus (minSG6-P1), An. maculatus (macSG6-P1) and An. dirus (dirSG6-P1)(GenScript, New Jersey, USA). Total IgG and IgM antibodies against Anopheles species-specific SG6-P1 antigens were measure using a highthroughput ELISA protocol. Detection of total IgG and IgM against salivary antigens was performed by adapting previously published ELISA protocols (29-31), and optimising them into a high-throughput protocol outlined below. Spectraplates (Perkin Elmer) were coated with 0.5µg/mL of Anopheles salivary peptides (Genscript) resuspended in autoclaved MilliQ water and diluted in PBS, and incubated for 3 hours at 37°C. Plates were washed and blocked for one hour at 37°C with Blocking Buffer (Pierce, Thermo Scientific USA). After a subsequent wash step, sera were added at a desired concentrations (diluted in 10% Blocking Buffer with PBS) and incubated overnight at 4°C. Following sera incubation, plates were washed and secondary antibody added. To detect human IgG and IgM, HRP-conjugated goat anti-human IgG (Millipore) and HRP-conjugated goat anti-human IgM (Millipore) was used at a 1:500 dilution. Plates were incubated at 37°C for 1.5 hours and then washed. ABTS (2,2'-azino-bis(3-ethylbenzothiazoline-6sulfonic acid)) substrate was added to each well, covered and left to develop at room temperature, then stopped with 1% sodium dodecyl sulphate (SDS), and the OD was read in a spectrophotometer at 405nm.

A minimum of 6 wells per plate were incubated with positive control sera consisting of pooled samples from naturally exposed participants found to have high levels of antibodies to *Anopheles* salivary proteins from a mass drug administration trial in Thailand (Positive Pool 1) and from our biting trial cohort (Positive Pool 2). A panel of negative control sera collected from individuals living in Melbourne with no history of malaria or travel to a malaria endemic region were also incubated in a minimum of 6 wells per plate. Additionally, each plate included 8 wells incubated without participant sera used to measure background reactivity.

In order to account for any variation between plates, plate-specific conversion factors were calculated and used to normalise OD values across multiple plates as follows. First, the mean OD of non-sera containing wells from each plate were subtracted from the OD of each sample to remove any background reactivity. Next, the mean of each positive control was calculated per plate and was then divided by the mean of that positive control calculated across all plates. Subsequently, the mean of these values on each plate was calculated to generate a plate-specific conversion factor. Finally, a normalised OD value for each sample was calculated by dividing it by the conversion factor for that plate. The OD of negative Melbourne controls was used to calculate the seropositivity thresholds. Seropositivity was defined as having a normalised OD greater than the mean OD of the negative controls plus three standard deviations.

Table 1. Anopheles salivary SG6-P1 peptide antigen amino acid sequences and their similarity to gSG6-P1.

Vector species	Antigen									F	Pept	tide	Sec	quei	nce										% gSG6-P1 Homology
An. gambiae	gSG6-P1	Е	К	V	W	٧	D	R	D	Ν	V	Υ	С	G	н	L	D	С	т	R	V	А	Т	F	-
An. dirus	dirSG6-P1	G	Q	Т	W	1	D	R	D	к	Т	Y	С	Е	н	1	D	С	Т	к	L	А	к	Y	48%
An. maculatus	macSG6-P1	Α	Κ	V	W	V	D	R	D	к	V	Y	С	Е	н	1	D	С	т	R	L	А	т	F	78%
An. minimus	minSG6-P1	Е	К	V	W	۷	D	R	D	R	V	Υ	С	G	н	Т	D	С	т	R	V	А	т	Y	87%

Note. Green shading references differences in amino acid sequence from gSG6-P1.

3.2 Inclusion-Exclusion Criteria and General Study Population

Participants will be randomised only if they fulfilled all the inclusion criteria and none of the exclusion criteria. These criteria were checked at the screening visit (Day -14 to Day -1).

Inclusion Criteria:

To be included in this study, an individual must satisfy all the following criteria:

- 1. Generally healthy male or female aged ≥ 18 to <60 years old as assessed by a medical doctor
- 2. Thai, Burmese or Karen ethnicity
- 3. Living in Mae Sot city for the last 12 months
- 4. Able to tolerate direct mosquito exposure

Exclusion Criteria:

If an individual meets any of the following criteria, they are ineligible for this study:

- 1 History of travel in a rural area (i.e., where participant may be exposed Anopheles bites) in the last 12 months, or plan to do so during the study
- 2 Medication or condition deemed to interfere with the outcome measure or increase the risk of an adverse reaction to the study procedures (hypersensitivity to mosquito bites, atopy, systemic mastocytosis, immunodeficiencies, Epstein-Barr virus-associated lymphoproliferative disease, and longue-course oral treatment with a steroidal anti-inflammatory drug)
- 3 Moderate and severe anaemia (haemoglobin concentration less than 110 g/L of blood)
- 4 Pregnancy
- 5 Breastfeeding

5.1 Randomisation and Blinding

A block randomization schedule will be generated using the block.random function of the R package psych version 1.8.12 (28) with variables species (*An. minimus, An. maculatus, An. dirus, Ae. aegypti* and *Ae. albopictus*) and dose (35 or 305 bites in total), yielding an ordered list of 15 blocks with 10 participants per block randomly assigned to one of the 10 study arms.

An allocation sequence will be implemented using individual, sealed and sequentially numbered envelopes. Following screening and eligibility assessment, participants will be assigned to a study arm during visit 2 using the randomization schedule.

An allocation sequence will be generated by a study investigator. At the beginning of the study, the study coordinator will prepare a set of case report forms (CRFs) with preprinted subject identification codes and attach the sealed envelope containing intervention allocation to the CRF. Study nurses will then assign a subject identification code to participants by chronological order of enrollment in the study and the envelope will be opened during visit 2.

Allocation of intervention will be masked to outcome assessors (laboratory personnel who will process the serum samples) and data analysts. In order to do so, allocation of intervention in study datasets that contain this information will be masked until the results of the final analysis are made available to study investigators.

Amendment to SAP 23/03/2023

In order to fit additional models assessing the effects of concordant vs discordant species of exposure on antibody analyses (detailed in Section 9.2), after consultation with Principal and Study Investigators, the antibody data were locked and the biostatisticians were un-blinded.

5.2 Study Visit Schedule

Study variables are collected according to the study visit schedule in Table 2.

Visit	Study period	Day ^a	Informed consent obtained	Medical History	PE and VS	Randomization	Mosquito exposure	DBS Collection	VP collection
1	screening	30 days or less before enrolment	Yes	Yes	Yes	No	No	No	Yes
2	baseline	0	No	No	No	Yes	No	Yes	Yes
3	baseline	7	No	No	No	No	No	Yes	Yes
4		14	No	No	Yes	No	Yes	Yes ^c	Yes ^c
5		15	No	No	Yes	No	No	No	No
6		21	No	No	Yes	No	Yes	Yes	Yes
7		22	No	No	Yes	No	No	No	No
8	exposure	28	No	No	Yes	No	Yes	Yes	Yes
9		35	No	No	Yes	No	Yes	Yes	Yes
10		42	No	No	Yes	No	Yes	Yes	Yes
11		49	No	No	Yes	No	Yes	Yes	Yes
12		56	No No Yes No		No	Yes	Yes	Yes	
13		63	No	No	No	No	No	Yes	Yes
14		70	No	No	No	No	No	Yes	Yes
15		77	No	No	No	No	No	Yes	Yes
16	post-	84	No	No	No	No	No	Yes	Yes
17	exposure	91	No	No	No	No	No	Yes	Yes
18		98	No	No	No	No	No	Yes	Yes
19		105	No	No	No	No	No	Yes	Yes
20		112	No	No	No	No	No	Yes	Yes

Table 2 Study Visit Schedule

^d 2 mL during the screening visit, 8.6 mL during visits 2, 3, 6, 8, 9, 10, 11, 12, 14, 15, 16, 17, 18 and 19 and 18.6 mL during visits 4, ^a In case participant fail to come on the exact day a visit is scheduled, he/she will be allowed to come for a retake any other working day of the study team until the next scheduled visit;

^b 5 bites for the screening of hypersensitivity to mosquito bites during visit 4, then 5 or 50 bites/visit according to the randomisation schedule (total of 35 and 305 bites/participant in low- and high-exposure groups respectively, split into 7 direct feeding assays);

^c before exposure to mosquito bites.

13 and 20.

6 Sample Size

There is no data to calculate the sample size *a priori* because the characteristics of immune responses to candidate peptides is not known at this stage. A sample size of 15 participants with complete follow-up per study arm was deemed appropriate for this study given the number of repeated assessments and expected variation in the continuous individual antibody responses. Participants with incomplete follow-up will be replaced to ensure there are 15 participants per study arm with complete follow-up.

7 General Considerations

7.1 Timing of Analyses

Study data entered and stored into the Excel files by the SMRU research team and assay data entered and stored in Excel files managed by the responsible laboratories will be transferred to researchers at the Burnet Institute and the Centre for Epidemiology and Biostatistics at the University of Melbourne (Melbourne, Australia). After the last subject has concluded study participation to Day 112 follow-up and all study data were available, the following topics were reviewed:

- 1. Study participants who have withdrawn consent, in relation to the use of the study participant's data (or part of it) in any of the analyses (Protocol Section 7.9). No subjects withdrew consent as part of the 112-day reporting period.
- 2. Subjects with (minor or major) protocol violations as defined in Section 8.3, in relation to the use of the subject's data (or part of it) in the per protocol analysis set (Section 8.3).

After the SAP is signed, the randomized exposure species and dose allocation will be obtained from the SMRU study team. No database may be locked, random code unblinded, or analyses completed until the SAP has been approved. The planned analyses in this SAP will be conducted after unblinding of the database and any changes to this SAP after unblinding will be documented in an amendment of this SAP and considered post-hoc analyses.

7.2 Analysis Populations

Study participants will be reported and analysed according to their randomisation order ("as-randomised"), except when mentioned otherwise. The following analysis populations are planned.

7.2.1 Intention To Treat Set

The Intention To Treat (ITT) Set consists of all enrolled participants who were randomised and provided at least one valid measurement of antibody response and will be analysed according to randomisation group.

7.2.2 Per Protocol Set

The Per Protocol Set consists of all participants included in the Intention To Treat Set who do not have any major protocol deviations (see Section 8.3).

7.3 Covariates and Subgroups

The protocol does not define any formal subgroup analyses.

7.4 Missing Data

Missing data will not be imputed, instead an available case analysis will be performed of the longitudinal outcomes, antibody levels and sero-prevalence.

7.5 Multiple Testing

There are no adjustments planned for multiple comparisons.

8 Summary of Study Data

Antibody data listings will be sorted by participant identifier and timepoint, as well as mosquito exposure species and biting dose, and enrolment month.

Data will be summarised as described in the sections below. Summaries will consist of descriptive statistics whereby continuous variables will be summarized using n (non-missing sample size), mean, standard deviation, median, minimum, and maximum and categorical variables using counts and percentages (based on the non-missing sample size) of observed category levels.

All confidence intervals (CIs) will be two-sided 95% CIs. Comparative analyses will consist of qualitatively describing the difference.

8.1 Subject Disposition

The flow of participants will be presented in accordance with the Consolidated Standards of Reporting Trials (CONSORT) criteria.

We will report the following:

- Number of participants assessed for eligibility
- Number of participants not meeting the inclusion criteria and declined to participate
- Number of participants allocated to each mosquito species exposure and dose group
- Number of participants attending day 112 visit and number of participants who withdrew from the study and lost to follow-up
- Number of participants included in the Intention to Treat Set and Per Protocol Set

8.2 Derived Variables

The following measures will be derived:

- Linear splines will be derived using the visit variable to represent the baseline (visits 2-3), exposure to *Anopheles* spp. bites (visits 4-12) and post exposure (visits 13-20) periods to model the boosting and decay of antibody responses.
- Exposure and post-exposure periods will be derived as a categorical time-varying variable.
- Concordant and discordant exposure species and antibody responses variables will be derived by collapsing across categories of the mosquito species participants were exposed to, according to the following groups: (i) exposure to *Anopheles* spp. compared to *Aedes* spp. (explored for all anti-SG6-P1 antibodies), (ii) exposure to *An*.

dirus bites, compared to *An. maculatus* and *An. minimus* bites, compared to *Aedes* spp. bites (explored for anti-dirSG6-P1 antibodies), (iii) exposure to *An. maculatus* bites, compared to *An. dirus* and *An. minimus* bites, compared to *Aedes* spp. bites (explored for anti-macSG6-P1 antibodies), (iv) exposure to *An. min* bites, compared to *An. maculatus* and *An. dirus* bites, compared to *Aedes* spp. bites (explored for anti-minSG6-P1 antibodies).

8.3 **Protocol Deviations**

The following will be considered as protocol deviations:

- Variation of Inclusion/Exclusion criteria
- Significant protocol deviations, which may have an effect on the integrity of study data

Protocol deviations were reviewed prior to un-blinding to determine which protocol deviations may affect the analysis. The Per Protocol Set will then be defined for the antibody endpoints with the following exclusions:

- Data from all available visits for subjects found to violate inclusion/exclusion criteria.
- Data from all visits subsequent for the protocol deviations that are considered to affect the integrity of the antibody data.
- Data from any visit that occurs substantially out of window.

Protocol deviations will not be excluded from the Intention to Treat Set, but may result in subjects being excluded from the Per Protocol Set. After review of the data prior to unblinding, no subjects were excluded from the Per Protocol Set.

8.4 Demographic and Baseline Variables

Demographic and baseline variables will be summarized, including age and sex, and presented by exposure species and dosing group using frequencies and percentages for categorical variables, mean and standard deviation and median (minimum – maximum) for continuous variables. If variables have missing values, we will report the non-missing sample either in the table or in the footnote of the table.

9 Statistical Analyses

9.1 Effect of mosquito biting exposure on antibody level and seropositivity

Measurement of mosquito species-specific antibodies will be using high-throughput ELISA are described in Table 3:

Assay	Visits	Outcomes
High-throughput ELISA	Visits 2-	Total Anti-IgG levels and seropositivity against:
	20	gSG6-P1
		minSG6-P1
		macSG6-P1
		dirSG6-P1
		aegNterm34kDa

Table 3 Overview of assays

Assay	Visits	Outcomes
		albNterm34kDa
High-throughput ELISA	Visits 2-	Total Anti-IgM levels and seropositivity against:
	20	gSG6-P1
		minSG6-P1
		macSG6-P1
		dirSG6-P1
		aegNterm34kDa
		albNterm34kDa
High-throughput ELISA	Visits 2-	Total antibody (including any isotype or subclass)
	20	levels and seropositivity against novel candidate
		Anopheles and Aedes species-specific antigens

Antibody markers will be summarised at each scheduled time point, including changes from baseline. Values will be presented visually with dotplots at each time point and spaghetti plots to visualise within-participant changes from baseline.

The change in antibody levels (as a continuous outcome and binary response) over time will be analysed using generalised linear mixed-effects models. Optical density measurements (*i.e.* antibody levels) will be analysed using a Gaussian distribution family and identity link function (*i.e.* a linear mixed-effects model) and binary responder status will be analysed using a Binomial distribution family and a logit link function (*i.e.* a logistic mixed-effects model). Linear splines will be fitted to represent the baseline (visits 2-3), exposure to mosquito bites (visits 4-12) and post exposure (visits 13-20) periods to model the boosting and decay of antibody responses. Mixed-effects models will include a random effect (*i.e.* intercept) for participant to allow random variations of immune responses in individuals. Estimates from the linear mixed-effects models will be used to calculate the half-lives of each antibody measure.

Amendment to SAP 23/03/2023

To account for positively skewed antibody data and aid interpretation, antibody levels were log₂ transformed to represent a two-fold change in antibody levels.

Due to differences (in terms of time) between individuals transitioning from baseline, to exposure and post-exposure periods, linear splines representing these periods of fixed time were unable to be estimated. Instead, the overall effect of time will be estimated (independent of any exposure and thus representing the baseline period), with the exposure and post-exposure periods fitted as a categorical time-varying variable. To estimate the extent to which antibody levels associated with biting are dependent on time, interaction terms for the intervention periods by time will be estimated.

The change in antibody levels (as a continuous outcome and binary response) over time, and in response to *Anopheles* biting exposure, will be analysed using generalised estimating equations (GEEs). The specification of an autoregressive correlation structure will better account for high-levels of serial correlation in antibody levels within individuals over time. Furthermore, a marginal model will allow for robust inference of the estimated effects of the exposure and post-exposure periods on antibody levels.

9.2 Moderating effect of mosquito biting species or dose of exposure on antibody level and seropositivity

To investigate if changes in antibody levels over time vary according to mosquito species or biting dose, interaction terms will be fitted between time, exposure species (*An. minimus, An. maculatus, An. dirus, Ae. aegypti* and *Ae. albopictus*) and biting dose (35 or 305 bites), respectively.

Amendment to SAP 23/03/2023

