10. STATISTICS AND ANALYSIS

10.1. The Number of Participants

There is no preliminary data to calculate *a priori* a required sample size. The groups are 15 participants (15 in the low-exposure and 15 in the high-exposure groups), and a comparison between these groups in expected. Because there is such variation in individual's antibody responses, and the specificity and immunogenicity of the antigens of interest is not known at this stage, it is important to ensure sure that any measured responses are not due to chance. Therefore, 15 participants per study condition was deemed appropriate for this study.

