This study is an exploratory, factorial randomized control trial of controlled exposure to mosquito bites with 10 arms corresponding to different species (*An. minimus, An. maculatus, An. dirus, Ae. aegypti* and *Ae. albopictus*) and numbers of bites (35 or 305 bites in total over 6 weeks). Participants will be assigned randomly to one of the 10 study arms with a 1:1 ratio using a block randomization schedule. Those with incomplete follow-up will be replaced until complete follow-up of 15 participants per arm is achieved. Serum from venous blood and capillary blood spotted on filter paper will be collected weekly from each study participant before, during and after the challenges. In addition to those described in the published literature, candidate peptides will be identified with antigen prediction algorithms using mosquito DNA sequences data (either deposited in open access databases (24) or generated using wild-caught mosquito specimens) and immunoproteomic assays carried out using protein extracts of dissected mosquito salivary glands and participants samples (20). Antibody titers will be determined with high-throughput ELISA (25) and mesoscale screening assays (26).

The Statistical Analysis Plan (SAP) for the analysis of "Characterizing antibody responses to mosquito salivary antigens of the Southeast Asian vectors of malaria and dengue with a human challenge model of controlled exposure" (ClinicalTrials.gov Identifier: NCT04478370) describes and expands upon the statistical information presented in the protocol.

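### As ordinarily fitted, the SAP 9.2 species, dose and concordance contrasts do not use the equality of pre-bite means that randomisation gives: a modest, avoidable loss of precision

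*SAP*

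**What the plan says.** SAP 9.2 studies whether changes in antibody level "vary according to mosquito species or biting dose, interaction terms will be fitted between time, exposure species" and biting dose. Its March 2023 amendment compares concordant and discordant species groups through interactions with the exposure and post-exposure periods. SAP 9.1, as amended, fits a GEE with an autoregressive correlation, an overall time effect, period as a time-varying factor, and period-by-time terms. Baseline is the reference period.

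Allocation is "with a 1:1 ratio using a block randomization schedule", revealed at visit 2 (SAP 5.1). The samples of days 0 and 7 precede the first bites. The day 14 sample (visit 4) does too: the note to SAP Table 2 says it is drawn "before exposure to mosquito bites". Protocol section 5 calls visit 4 baseline for the immuno-proteomic work, yet SAP 8.2 and 9.1 place visit 4 in the exposure period.

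The only adjustment variables named (Protocol 10.2) are age, sex and biting exposure group. Neither document adjusts for the pre-bite antibody level or sets it equal across arms. Neither says whether species and dose main effects are fitted alongside the interactions.

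On size, the SAP states "There is no data to calculate the sample size" in advance, and 15 per arm was judged appropriate.

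**The concern.** A group-by-period interaction fitted with a group main effect is a difference in differences: each arm's pre-bite mean is estimated freely and then subtracted in full. In a randomised comparison the true pre-bite means are equal, so this spends information on a quantity known to be zero in expectation. It also carries the noise of two or three baseline samples into every contrast. Adjusting for the pre-bite level, or constraining its mean to be common, normally avoids that.

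The stake is the width of the dose, species and concordance intervals, not their validity. It deserves attention because arms hold 15 people, there is no power target, and the protocol itself stresses the spread of responses ("Because there is such variation in individual's antibody responses"). The dose-response relation is a named secondary objective.

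**Working it through.** **The plan's own figure.** 10 arms x 15 = 150, as stated; 5 x 15 = 75 per dose and 2 x 15 = 30 per species. No SD, effect or power is given, so only relative variances can be computed. Total SD is set to 1. All correlations are assumptions, because SAP 9.1 says only that serial correlation is high.

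**Step 1: period means.** Let va be the variance of a person's mean in a bite or post-bite period, vb that of the pre-bite mean, and c their covariance.
- Change: va + vb - 2c.
- Baseline-adjusted: va - c²/vb.
- The difference is (vb - c)²/vb, never negative, so adjustment of period means cannot lose in large samples.

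Stable person effect only, r = 0.8, three pre-bite and eight post-exposure samples:
- post-exposure mean alone: 0.8 + 0.2/8 = 0.825;
- change: 0.2 x (1/3 + 1/8) = 0.0917, which is 0.11 of 0.825;
- adjusted: 0.825 - 0.64/(0.8 + 0.2/3) = 0.0865;
- adjusted/change = 0.94.

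Here the change contrast already captures most of the baseline information.

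Decaying correlation, AR(1) 0.90, post-exposure: va = 0.773, vb = (3 + 4 x 0.9 + 2 x 0.81)/9 = 0.913, c = 0.308. Change = 1.07, adjusted = 0.67, ratio 0.63.

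**Step 2: the planned kind of model.** GEE with AR(1) working correlation, 17 weekly samples, common time and period-by-time terms, group entering through period, three pre-bite samples, 75 per dose. The sandwich variance is A⁻¹BA⁻¹, with A = ΣX'W⁻¹X and B = ΣX'W⁻¹SW⁻¹X. It is computed with a free group main effect and then without one (common pre-bite mean).

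| Assumed correlation | Exposure: free, common, ratio | Post-exposure: free, common, ratio |
|---|---|---|
| AR(1) 0.80 | 0.0098, 0.0072, 0.73 | 0.0166, 0.0103, 0.62 |
| AR(1) 0.90 | 0.0052, 0.0046, 0.88 | 0.0097, 0.0080, 0.82 |
| AR(1) 0.98 | ratio 0.99 | ratio 0.98 |
| Person share 0.8 + AR 0.5 | 0.0048, 0.0045, 0.95 | 0.0083, 0.0077, 0.93 |
| Person share 0.9 + AR 0.8 | ratio 0.98 | ratio 0.97 |

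With visit 4 left in the exposure period (two pre-bite samples), the ratios are 0.87/0.81 at AR(1) 0.90 and 0.70/0.60 at 0.80. Since √0.88 = 0.94 and √0.82 = 0.91, intervals at AR(1) 0.90 are about 6% and 9% narrower.

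**Step 3: two limits found on checking.**
- *Group slopes.* If groups may also differ in slope within each period (contrast taken at mid-period), the constraint gains more when AR(1) is true: 0.79/0.61 at 0.90. If the truth has a large stable person share but the working matrix is pure AR(1), it can lose: 0.96/1.22 at person share 0.7 + AR 0.7, and 1.12/2.04 at 0.8 + 0.5. With a working matrix that matches the truth, these cases give 0.90/0.86 and 0.93/0.91.
- *Covariate version.* Using the mean of three pre-bite samples as covariate, with post-bite records only, is not sure to beat the planned GEE. Under decay the last pre-bite sample carries most of the information. At AR(1) 0.90, with group entering through period, the ratios were 1.77/1.18.

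**The case against.** A reader might infer that the plan ignores the pre-bite level. It does not. Visits 2 and 3 are outcome records, baseline is the reference period, and the contrasts are of changes. When correlation is high and stable this recovers nearly all the available information.

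A reader might also infer a gain worth 1.1 to 1.6 times as many participants. The upper end is 1/0.63, for equally weighted period means under pure AR(1) 0.90. That is not the planned model, and the lower end is nearer 1.03 when correlation is mostly a stable person effect (1/0.97).

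Free arm means are an ordinary reading of 9.2, not a stated choice. If main effects are absent, the model is already the constrained one.

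Equality of pre-bite means is also not perfect. Withdrawn participants are replaced within the same arm (Protocol 7.9), so replacements are not freshly randomised. Larval-source counselling goes only to Aedes participants (Protocol 7.2), and the day 7 and 14 samples follow allocation. Any effect is probably small, but it justifies a sensitivity analysis.

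Finally, the trial is exploratory and the SAP describes differences qualitatively, so no stated figure changes. All of this stands and limits the point to a precision gain. It does not remove the case for stating how baseline arm means are handled.

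**Conclusion.** The planned analysis is valid; this is a cheap improvement, not an error. If arm main effects are fitted, a common pre-bite mean would cut the variance of the continuous between-arm contrasts by about 12% (exposure) and 18% (post-exposure) at AR(1) 0.90. The cut is 27% and 38% at 0.80, 5% and 7% with person share 0.8 + AR 0.5, and 1-3% when correlation is nearly all stable or AR(1) is 0.98. It is nil if main effects are already omitted. These sizes rest on assumed correlations, three pre-bite samples, and group effects that enter through period. With group-specific slopes, a gain can be relied on only if the correlation model allows a stable person effect. The figures do not carry over to seropositivity.

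**What to change.** For log2 OD in SAP 9.2:

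1. Write out the model equation. Keep all samples, count the day 14 pre-bite sample as baseline, and omit the species, dose and concordance main effects. Groups then share one pre-bite mean and differ only through interactions with period and time.
2. Before fitting group-by-period-by-time terms, inspect the correlation at long lags. If it levels off, use a structure with both a person effect and decay, such as a random intercept with AR(1) residuals, with robust standard errors.
3. As a sensitivity analysis, given same-arm replacement and Aedes-only counselling, compare post-bite samples adjusted for each participant's mean pre-bite log2 OD. Do not keep baseline visits as outcomes in that model, which would use the same data twice.
4. Leave the 9.1 period-effect model as it is; it needs the pre-bite records to identify the time effect.
5. Do not add a baseline covariate to the logit seropositivity model without noting that it changes the estimand.
6. Record this as a dated amendment. The biostatisticians are unblinded (SAP 5.1), and SAP 7.1 makes later changes post hoc.

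Cost: a little extra modelling and the post hoc label. No new data are needed.
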